3.2.2 Phase II: Secondary Objectives

- 1) Confirm safety of phase II dose of ONC201 in combination with Opdivo (Nivolumab) using CTCAE version 5.0
- 2) Assess preliminary overall survival associated with ONC201 and Opdivo (Nivolumab) in patients with microsatellite stable metastatic colorectal cancer
- 3) Correlate clinical outcome with tumor & blood biomarkers including cancer stem cells, signaling intermediates and inhibitors, NK cells, TRAIL, granzyme, perforin, and M30.

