4.4 Duration of Study

A cycle is defined as q 4 weeks (28 days). Nivolumab and ONC201 will start on day 1 of each cycle (following an initial dose of ONC 201 on day -7). ONC201 will be given weekly day 1, and Nivolumab will be given q 2 weeks at a flat dose of 240mg IV over an approximate 30-minute infusion. See treatment section for details.

Dosing will continue until disease progression, unacceptable toxicity per patient or treating physician, or the patient discontinues for any other reason.

The maximum duration of treatment will be 12 months unless it is determined that a patient would derive benefit from continued therapy beyond 12 months, as determined by the investigator. Follow-up for all patients will be approximately 6 months.

The study is expected to be completed over an approximate 3.5-year period

When patients discontinue study treatment, they should return to the study site 30 days (+1 week) and 100 days (+1 week) after administration of the last treatment (Nivolumab or ONC201, whichever is last) to complete the safety assessment visit and procedures.

The study will be completed in approximately 3.5 years, taking into account approximately 2 years of enrollment, 12 months of treatment and approximately 6 months of follow-up, on average.

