¹¹ cfDNA: blood to be collected at baseline (pre-dosing ONC201, prior to day -7 cycle 1) and prior to ONC201 and Nivolumab (twice a cycle with pre-Nivolumab labs) cycles 1-6. Cycles 7-on: CfDNA will be collected pre-dosing each cycle day 1 only. CfDNA will not be collected once patient progresses. If patient remains on study post 12 cycles, cfDNA will only be drawn pre-dosing day 1 of each cycle: **Collect CfDNA whole blood sample in 1 K2EDTA tube. Post collection, invert sample 8-10 times and let site at room temperature. See section 11.1.3.**

¹² Subjects providing informed consent will have tumor biopsy performed pre-treatment, at approximately 8 weeks when the first tumor imaging assessment is performed, and at the time of progression. For those patients whose disease is progressing at the first post-treatment imaging assessment at 8 weeks they will only have 2 biopsies.

¹³ Tissue from a biopsy (at least 3-6 cores in 10% neutral buffered formalin) will be obtained by radiologic guidance and sent to the laboratory of [name]. Only 2 biopsies will be required for patients who progress at the end of cycle 2.

¹⁴ Off-study evaluation to occur post completion of entire cycle. Follow-up visits or other contact are required in order to identify SAEs during the first 100 days (+1 weeks) following the end of study treatment (Nivolumab, or ONC201), respectively. There will be a safety visit at 30 days (+1 week) and 100 days (+1 week) time points. SAEs need to be reported after 100 days if the SAE is thought to be related to study treatment. 30-day and 100-day safety evaluation time points required for all patients who receive at least one dose of drug on BrUOG 379, unless they withdraw consent.

¹⁵ Survival and disease status will be collected for all patients who receive at least one dose of ONC201 once they come treatment (unless they withdraw consent), approximately every 3 months for (+/- 1 month) 6 months

¹⁶ EKG registration and as clinically indicated. Any findings from EKGs collected after initiation of study treatment will be captured as AEs if, in the opinion of the investigator, there has been a clinically significant change from baseline.

¹⁷ Medications used by the patient and therapeutic procedures completed by the patient will be recorded in the CRF from screening through 100 days after the last dose of study drug or the start of subsequent antineoplastic therapy, whichever occurs first.

9 Criteria for Taking a Participant Off Protocol Therapy

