16.3 Efficacy Analysis for Phase II

All patients who have received a minimum of 1 cycle of study treatment, had baseline assessments

and at least one on-study tumor assessment will be considered evaluable for response.

Response rate is defined as the proportion of patients with a Complete (CR) or Partial Response (PR) relative to the total number of evaluable patients. Responses will be defined according to the RECIST version 1.1 guidelines for solid.

The best overall response is the best response recorded from the start of treatment until disease progression/recurrence (taking as reference for progressive disease the smallest measurements recorded since the treatment started) or the withdrawal from the study. Stable disease will be considered the best response when observed at least after two months from baseline. Tumor responses will be analyzed in a descriptive manner. The number and percentage of objective response (CR+PR) will be tabulated. Response rate may be summarized with the corresponding 95% exact confidence interval.

Progression free survival will be defined as the number of days between the first treatment with protocol specified therapy and death or progression, whichever comes first. Individuals who are alive and progression free at last contact will be censored at that time.

Overall survival (OS) will be defined as the number of days between the first treatment with protocol specified therapy and death. Individuals who are alive at last contact will be censored at that time.

Progression free survival and overall survival time distributions in the Phase II study population will be summarized using the methods of Kaplan and Meier.

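### Survival contact stops about 6 months after each patient leaves treatment, so OS follow-up depends on outcome: many deaths go unobserved and the late Kaplan-Meier curve is probably somewhat too high

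*Combined protocol and SAP*

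**What the plan says.** Overall survival is a phase II secondary objective (section 3.2.2): "Assess preliminary overall survival associated with ONC201 and Opdivo (Nivolumab)". Section 16.3 summarises it by Kaplan-Meier, with this censoring rule: "Individuals who are alive at last contact will be censored at that time". Section 10 has a parallel definition that censors at the date last known alive.

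Section 8, footnote 15 governs collection: "Survival and disease status will be collected for all patients who receive at least one dose of ONC201 once they come treatment", then "approximately every 3 months for (+/- 1 month) 6 months". Section 4.4 restates the limit: "Follow-up for all patients will be approximately 6 months". The same 6-month statement appears in sections 4.2, 6.2 and 8.

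Section 4.4 says what ends treatment: "Dosing will continue until disease progression, unacceptable toxicity per patient or treating physician, or the patient discontinues for any other reason". It also sets a ceiling, "The maximum duration of treatment will be 12 months", which the investigator may extend. Its timeline reads: "The study will be completed in approximately 3.5 years, taking into account approximately 2 years of enrollment", with 12 months of treatment and about 6 months of follow-up making up the rest.

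Nothing in the protocol takes survival contact to a common cutoff, to a fixed time from first dose or to death, and nothing in the analysis allows for dependent censoring. The 30-day and 100-day safety contacts end sooner than the 6-month survival contact, so they do not fill the gap.

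**The concern.** Kaplan-Meier treats a patient censored at a given month as having the same later risk of death as those still followed. Here the follow-up rule decides who is censored, and it works through progression. Between about months 8 and 18, the patients removed alive are those who left treatment early, usually with progressed disease. Those retained include patients who stayed progression-free for longer. The late risk set is therefore selected.

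Two things are at stake. Deaths more than 6 months after treatment need not be recorded, although the study remains open for about 3.5 years. The later part of the OS curve also rests on few, selected patients. With one arm, anyone using that curve will probably set it against outside figures. Wide sampling error shows in a confidence interval; dependent censoring does not. Any biomarker correlation that uses OS as the outcome loses the same deaths.

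**Working it through.** **Inputs from the documents.** Follow-up of 6 months after treatment ends (section 8, footnote 15). Scans every 8 weeks (section 8, footnote 3). Usual treatment maximum of 12 months and accrual of about 2 years (section 4.4). 34 patients at the RP2D (section 16.2.1). PFS of 50% at 3 months under the null, and 71% (median 6 months) under the alternative (section 16.4).

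**Assumption.** The documents do not give post-progression survival. Medians of 3 to 12 months were examined, with 6 months as the base case.

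**Plan's own figures.** Duration: 2 + 1 + 0.5 = 3.5 years, as stated. PFS at 3 months: 0.5^(3/3) = 50% and 0.5^(3/6) = 70.7%, matching the stated 50% and 71%.

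**Length of follow-up.** Off treatment at the first scan: 8 weeks is about 1.8 months, and 1.8 + 6 = 7.8, so about month 8. Full treatment: 12 + 6 = month 18.

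**True OS, base case.** With independent exponential PFS (median 3) and post-progression survival (median 6), S(t) = 2x − x², where x = 2^(−t/6). At 12 months x = 0.25, so S = 0.50 − 0.0625 = 43.8%. The median solves 2x − x² = 0.5: x = 0.293 and t = 10.6 months.

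**Kaplan-Meier under the plan.** Simulation of 400,000 patients: progression detected at the next 8-week scan, censoring 6 months after leaving treatment.

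| Month | True OS | Kaplan-Meier | Difference (points) |
|---|---|---|---|
| 6 | 75.0% | 75.0% | 0 |
| 9 | 58.2% | 58.7% | +0.5 |
| 12 | 43.8% | 46.0% | +2.2 |
| 15 | 32.2% | 35.9% | +3.7 |
| 18 | 23.4% | 28.1% | +4.7 |

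The estimated median is 11.0 months, against a true 10.6.

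**Information lost, base case.** About 45% of patients are censored alive (47% if the 12-month treatment maximum is applied), or 15 to 16 of 34. With follow-up to a common close at 42 months and uniform 2-year accrual the figure is 8%, about 3 of 34. The mean number at risk at 12 months is 6.8 of 34, against about 34 × 0.4375 = 14.9. Over PFS medians of 2 to 6 and post-progression medians of 4 to 8 months, about 10 to 22 of 34 deaths go unobserved under footnote 15, against 1 to 8 with the common close.

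**Range of the bias under independence.** Zero at 6 months, at most +0.7 points at 9 months, +0.9 to +2.6 at 12 months and +1.3 to +7.5 at 18 months. With both medians at 6 months, true 18-month OS is 0.125 × (1 + 2.079) = 38.5%, and Kaplan-Meier gives 45.9%.

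**Other dependence structures.** If early progressors also die sooner after progression (medians 4.5 and 9 months), 15-month OS is 40.6% against a true 34.3%, and the median is 11.3 against 10.5 months. Over 36 sensitivity scenarios, the 18-month bias was upward in 31, reaching +15.8 points. In the other 5 it was near zero or slightly negative (to −2.1 points); all had median PFS of 3 months with a falling post-progression hazard or a negative correlation.

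**The case against.** The case against concerns strength rather than fact.

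- **Direction.** A reader might infer that OS is certain to be overstated. That does not follow: the sign depends on post-progression survival, which the documents do not give, and 5 of 36 scenarios were not upward. This objection stands.
- **Size.** At 12 months the base-case bias is about 2 points, while the sampling SD of the estimate with 34 patients is about 10 points. Bias is thus the smaller problem there. The loss of precision is larger: at 15 months the SD is about 11.5 points, against about 8 with a common cutoff.
- **Treatment beyond progression.** Section 10 allows it, which starts the 6-month clock later. If 40% of patients continued for one more scan (an assumption), the 12-month bias would fall from +2.3 to +1.4 points and the 15-month bias from +3.8 to +2.7. Follow-up is also only approximate: at 7 months the 12-month bias is +1.2, and at 5 months +3.6. These points change the size, not the mechanism.
- **Analysis rule.** Section 16.3 censors at last contact and section 10 at the date last known alive, so a later contact would count if it happened. This helps only partly, because none is required.
- **Importance.** OS is preliminary and descriptive. The plan states no OS hypothesis, event target, power or historical OS benchmark. A reader might infer that the bias corrupts a planned historical comparison, but the documents contain none; the risk lies in informal use of the curve.

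**Conclusion.** The concern holds in a limited form. Follow-up for OS depends on outcome, because the 6-month clock starts when treatment ends and treatment normally ends at progression. The non-informative censoring that Kaplan-Meier needs is therefore not met, and nothing in the plan corrects for it.

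The firmest consequence, and the main one, is the loss of deaths and of patients at risk, which occurs whatever the sign of the bias. Upward bias after about month 8 is expected but not certain. It is modest at 12 months and larger in the tail, and larger still if early progressors also die sooner after progression. All these sizes rest on assumed post-progression survival.

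It would be wrong to read this as discrediting the whole OS curve, since the part to about 6 months is unbiased. It would also be wrong to carry it over to the trial's efficacy decision: the co-primary rules use response and 3-month PFS, which this does not touch. The change is a cheap improvement to a secondary endpoint, best made prospectively because deaths after contact lapses may not be recoverable.

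**What to change.** In section 8, footnote 15, and the matching 6-month sentences in sections 4.2, 4.4, 6.2 and 8, separate survival status from the rest of follow-up. Collect it by phone or record check about every 3 months until death, withdrawal of consent, or one calendar cutoff common to all patients.

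Fix that cutoff in advance within the planned study period, for example 3.5 years after first enrolment. With 24 months of accrual, the last patient enrolled would still have 42 − 24 = 18 months of potential follow-up. Do not tie the cutoff to the last patient ending treatment: treatment may be extended beyond 12 months, so such a date could run past 3.5 years.

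In sections 16.3 and 10, censor OS at that cutoff, or at the date last known alive if the patient is lost earlier. Censoring by calendar date depends on when a patient enrolled, not on when the patient progressed. In the simulations this removed the bias, as it must when entry date is unrelated to prognosis.

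Cost: an amendment, consent wording, and some further phone or chart checks for roughly 15 of 34 patients (base case). It adds no visits, scans or study time and changes no treatment rule.

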11 BIOMARKER, CORRELATIVE, AND SPECIAL STUDIES

11.1 Pharmacokinetic Evaluations

During phase IB, plasma samples will need to be prepared from blood collected in K2EDTA tubes at baseline (pre-cycle 1 day 1), day 1: 30 minutes, 2, 4, 6, 24, 48, and 168 hours following the first two cycles of ONC201 and pre-dose on day 1 of subsequent cycles (through cycle 12 only). See schedule of evaluations for windows on each draw.

Pharmacokinetic samples will be collected and stored in the laboratory of [name] [name] and processed at a later time.

Collect PK samples in one K2EDTA 5mL tube. Gently invert the tube 8 times after draw and maintain at room temperature.

One K2EDTA tube (5mL) will be collected per time point. Each tube will be labeled as follows:
BrUOG 379
Patient initials

Page 83 of 145

Protocol- BrUOG 379

CONFIDENTIAL

Dates: 11/04/2018, 11/11/18, 11/16/18, 11/24/18, 11/30/18, 12/2/18, 12/6/18, 12/7/18, 12/10/18, 1/8/19 BMS review, 1/9/19, 1/13/19, 1/15/19, 1/16/19, 1/17/19, 1/20/19, 1/22/19, 2/4/19, 2/19/19, 3/19/19, AM#1 7/22/19, BMS review 8/23/19, AM#2 3/3/20, BMS approved 4/1/20, Oncoceutics approved 4/24/20, AM#3 10/26/2020, BMS approved 1/5/21, Oncoceutics approved 3/30/21

Patient study number

PK sample

Time point

Time 24-hour clock

As part of understanding the pharmacokinetics of the study drug, samples may be used for metabolite identification and/or evaluation of the bio-analytical method. These data will be used for exploratory purposes and will not be included in the clinical report.

Prior to transporting samples, an email is to be sent from a member of the Lifespan Oncology Clinical Research Office to a member of [name] lab (Email: [contact]) at least 24 hours prior to the collection of the sample(s). The email is to reference the patient initials and BrUOG 379 patient number, time point and samples. The lab will be informed that the sample will be transported post collection on <insert date>. This email is required to be de-identified and submitted to BrUOG with cycle data.

Blood must be sent to the research lab immediately after collection at ambient temperature. Please call [name] at [contact] when samples are available.

Lab address:

[name]

[name]

[name]

11.1.1 Background

Molecular markers involved in the molecular mechanism of ONC201 will be assessed on available tumor tissue and serum specimens as described below.

11.1.2 Biomarkers in Blood: PD samples

In addition to pharmacokinetics, this study will preserve samples at the laboratory of [name] to conduct future correlative assays to measure biomarkers of therapeutic response to ONC201 including molecular markers involved in the mechanism of action of ONC201. For each patient, 1 tube of 5 mL of blood will be collected in red-top tubes (no anti-coagulants).

During phase IB and II, blood samples for PD analyses will need to be collected at baseline (pre-cycle 1 day 1), day 1: 6 hours, 2, 3, and 7 days after ONC201 treatment for cycles 1 and 2, and at pre-dose on day 1 for cycles 3 and beyond. Caspase-cleaved cytokeratin 18 (cCK18) will be measured as a biomarker of epithelial cell apoptosis and prolactin will be measured as a surrogate biomarker of DRD2 antagonism (Diapharma; #P10011). The 7-day collection is the same as pre-dose after the first dose on the weekly ONC201 schedule (this aligns with day 8). See schedule of evaluations for windows on draws. Patients who remain on study post 12 cycles, PD samples will be drawn pre-dosing day 1 each cycle.

Each sample will be drawn in one red-top with no anti-coagulant. The sample should clot, there is no processing to be done prior to the transport of the sample to the laboratory.

One red-top tube with no anti-coagulant, will be collected per time point. Each tube will be labeled as follows:

BrUOG 379

Patient initials

Patient study number

PD sample

Time point

Time 24-hour clock

Analysis of circulating tumor cells for enumeration and molecular analysis is also permitted.

Prior to transporting samples, an email is to be sent from a member of the Lifespan Oncology Clinical Research Office to a member of [name] lab (Email: [contact]) at least 24 hours prior to the collection of the sample(s). The email is to reference the patient initials and BrUOG 379 patient number, time point and samples. The lab will be informed that the sample will be transported post collection on <insert date>. This email is required to be de-identified and submitted to BrUOG with cycle data.

Blood must be sent to the research lab immediately after collection at ambient temperature. Please call [name] at [contact] when samples are available.

Lab address:

[name]

[name]

[name]

11.1.3 CfDNA:

Blood samples need to be collected for CfDNA analysis at baseline (pre-cycle 1 day 1), then every two weeks while on study cycles 1-6, pre-ONC201 and on same days as Nivolumab dosing (prior to dosing day 1 and day 15). In cycles 7-12, CfDNA will be drawn pre-dosing day 1 each cycle only. CfDNA will be drawn until progression. If a patient remains on study post 12 cycles, sample to be drawn prior to dosing day 1 each cycle only (cycles 13+).

Each tube will be labeled as follows:

BrUOG 379

Patient initials

Patient study number

CfDNA sample

Time point

Time 24-hour clock

Prior to transporting samples, an email is to be sent from a member of the Lifespan Oncology Clinical Research Office to a member of [name] lab (Email: [contact]) at least 24 hours prior to the collection of the sample(s). The email is to reference the patient initials and BrUOG 379 patient number, time point and samples. The lab will be informed that the sample will be transported post collection on <insert date>. This email is required to be de-identified and submitted to BrUOG with cycle data.

CfDNA samples: Whole blood to be collected in one K2EDTA tube each time point. Post collection, site personnel is required to invert sample 8-10 times and then let sit at room temperature until sent to laboratory. Blood must be sent to the research lab immediately after collection at ambient temperature. Please call [name] at [contact] when samples are available.

Lab address:

[name]

[name]

[name]

11.1.4 Biomarkers in Tumor Biopsy

Archival Tissue:

Research Biopsies: patients will undergo up to 3 biopsies on study.

- 1) Prior to dosing: Required post consent and pre-ONC201 run-in dose
- 2) At the beginning of cycle 3 (approximately 2 months) to align with imaging
- 3) If patient was found to not progress at 2 months (1st scan), then 3rd biopsy would be completed at time of progression (if patient progresses during follow-up time period). This biopsy is optional.

Tumor biopsies will be taken (pre-treatment and at the first imaging assessment post-treatment at 8 weeks of the combinatorial regimen, and again at the time of progression).

Tumor biopsies will be performed using 18G core biopsy needles (or as per standard radiologic procedures) and limited to 1–2 passes for each sample to reduce risk of hemorrhage and fine needle aspirations using 23G needles (or as per standard radiologic procedures) with immediate bedside cytopathological confirmation of presence of tumor cells.

Based on some preclinical studies, the 48 post-treatment time point is adequate to measure

induction of ATF4 & CHOP, as well as DR5 & TRAIL induction. Preclinical studies with ONC201 have implicated many proteins such as ATF4, CHOP, DR5 and TRAIL as drivers of the anti-tumor activity of ONC201. Changes in the expression of these markers will be assessed by immunohistochemistry at baseline and post-treatment. In addition, changes in key apoptotic proteins such as caspases and PARP will be carried out. Thus, we will correlate clinical outcomes with tumor & blood biomarkers including cancer stem cells, signaling intermediates and inhibitors, NK cells, TRAIL, granzyme, perforin and M30. NK cells in blood will be assessed in the phase Ib portion at similar time points as PK studies and then later in phase II.

Tissue biopsies will be subjected to immunohistochemistry for CHOP (Proteintech; # 5204-1-AP), DR5 (Novus; NB100-56618), CD56 (BioLegend, Catalog X), Granzyme B (Abcam; Catalog X) and TUNEL (Novus; #NBP2-31164) as per the manufacturer's instructions on slides prepared from formalin-fixed paraffin-imbedded tissue. NGS and RNA-seq will be performed on pre- and post-treatment biopsies looking for markers of sensitivity as well as mechanisms of resistance. A major goal is to understand the differences between responders and non-responders. Researchers will analyze T-cell and NK cell content of the tumor biopsies. PD1 and PD-L1 testing will also be performed.

For tissue from research only biopsy:

The research staff is to contact [name] laboratory (to submit de-identified email chain with data to BrUOG) at least 24 hours prior to collection of a research only biopsy. [name] laboratory will be contacted by a member of the research team once the biopsy has been completed to retrieve the biopsy specimen (Email: [contact]). Once the biopsy is complete, the Cancer Center research staff will be notified for pick-up of material. The tissue must be labeled with study number (BrUOG 379), patient initials, patient study number and time point.

Each tissue biopsy is to include 3-6 cores and be stored in 10% neutral buffered formalin.

Tissue to be sent to the research lab once collected. Please call [name] at [contact] when tissue is available.

Lab address:
[name]
[name]
[name]

